Specifically, this study aims at predicting 2 target outcomes: acute exacerbations of COPD (AECOPDs) as defined by the GOLD initiative, and the CAT score as a proxy for patients' disease status. The start of an exacerbation within a patient, regardless of how many exacerbations the patient may have experienced before, will be predicted based on sensor data preceding the

exacerbation, and using basic covariates as well. For type of exacerbations, the severe and moderate exacerbations are considered as our main target as these are linked to the need of urgent medical intervention and will predict those as a group, but also separately (distinguish by type), if possible. Mild exacerbations, the relevance of which is currently a subject of investigation in the field, will also be explored.

For the CAT score, the aim is to predict the total score (max = 40) from the sensor data, and changes in the CAT score of ≥ 2 based on the MCID. With this approach, it is aimed to use the model built on sensor data as an objective means to reflect patients' disease status. While for the prediction of exacerbations the aim is to predict them as early as possible, i.e. days before an exacerbation, for the CAT/disease status prediction the aim is to reflect the daily status.

CCI

This study is exploratory in nature and any predictive models will need to be validated in future studies. A future remote patient monitoring (RPM) solution for patients with COPD built on these models will have 2 prime utilities: First, ameliorating or preventing exacerbations and their negative sequelae by early treatment intervention and second, to provide physicians and patients with a highly granular and precise view on the current disease status and past changes. Such information can be used by the treating physician to optimize therapeutic regimens and by the patients to accompany and optimize lifestyle changes. By using a multimodal sensor approach we intend to increase the accuracy of our predictive models beyond what has been described in the literature and thereby increase their clinical utility.

8 Research Question and Objectives

The aim of the study is to investigate the correlation of real-world sensor-derived biometric data obtained via a wearable device with clinical parameters and PROs for monitoring disease activity and predicting exacerbations for patients with COPD.

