9.7.2.2 Secondary Objectives

Secondary Objective 3):

To evaluate the correlation of sensor collected data with

- a) patients' self-assessed health status and symptoms (CAT) at baseline and study end,
- b) lung function and lab values at baseline and study end,
- c) and with history of moderate and severe exacerbations at study end

This analysis will be performed on the COPD participants set.

Coefficients of correlation with 95% CI of sensor collected data on physical activity, heart rate, heart rate variability, temperature, respiration rate, cough frequency, sleep pattern with patients' health status (CAT) at baseline (Day 0) and study end, lung function (e.g. FEV1) at baseline

(Day 0) and study end, laboratory values at baseline (Day 0) and study end and with moderate and severe exacerbations throughout the observation period.

- **Secondary Objective 4):** Sensor derived data may be related to the CAT score, therefore, an additional objective is to investigate whether changes in physical activity, heart rate, heart rate variability, temperature, respiration rate, cough frequency, and sleep pattern in the 3-month observation period, are associated with changes of the patient self-assessed symptoms (CAT).

This analysis will be performed on the COPD participants set using correlation maps and linear models as appropriate.

Secondary Objective 5): To predict the CAT score and changes thereof by building a statistical model employing sensor-derived data and demographic and medical covariates.

[figure not shown]
[figure not shown]
To build a model based on sensor-derived data, demographic and medical covariates to predict:

- patient self-assessed symptoms (CAT score measured on a daily basis)
- change of CAT score by 2 points or more (considered as MCID).

[figure not shown]
This analysis will be performed on the COPD participants set.

Different machine learning algorithms will be evaluated, and their performance will be assessed by estimating their accuracy, specificity, sensitivity, and area under receiver operator curve (ROC) metrics.

CCI

CCI

Data analyses will employ SAS (Version 9.4 or higher), JMP (Version 16.2 or higher), R (Version 4.2 or higher) and Python (Version 3.8 or higher).

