Different machine learning algorithms will be evaluated, and their performance will be assessed by estimating their accuracy, specificity, sensitivity, and area under ROC metrics. Other usual evaluation metrics such as precision, positive predictive value (PPV), negative predictive value (NPV), F1-score will be computed.

This analysis will be performed on the COPD cohort. Internal cross-validation will be tested.

The following models will be used:

- Logistic regression
- Random Forest
- K-nearest neighbors
- Boosting methods (e.g., Gradient boosting machine, GBM)
- Support vector machines (SVM)

Other methods may be tested.

The development of those models will be based on the machine learning algorithms implementation of scikit-learn (12), a python package designed for predictive data analysis. Other packages may be considered if needed (e.g., H2O (13)).

To optimize the performance of the models, feature extraction and selection algorithms will be used.

Explanatory models will be built on top of the selected machine learning algorithm (14), as a way to support rationalization for physicians and regulatory organizations. Depending on the selected ML model selected, either model specific (for logistic regression, decision trees, k-nearest neighbors) or model agnostic methods will be considered (global methods as PDP, ALE, functional decomposition, and local methods as LIME and Shapley values).

### 3.4.5.3 Secondary Objective 3

Objective 3 will be analyzed on the COPD cohort. For each pair of variables and outcomes ( $x, y$ ) defined below, Pearson's correlation coefficient will be computed together with a 95% asymptotic confidence interval based on Fisher's Z transform.

In case of low variability in parameter values (e.g., exacerbation count), parameters may be treated as ordinal and analyzed in terms of Kendall's Tau statistic with non-parametric confidence interval (see (15)).

The following variable groups and outcomes will be paired and assessed at the indicated time points:

Group x	Group y	Time points for assessment
Sensor data (see section 2.1.4), daily averages (17 variables): physical activity, heart rate, resting heart rate, heart rate variability, temperature, respiration rate, ratio of in- vs expiration time, cough frequency, sleep pattern (hours of sleep)	CAT summary score: Self-assessed patient's health status by CAT questionnaire.	Baseline (Day 0), End of study visit

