- The analysis above will be repeated on the COPD participants with severe/moderate exacerbations in the time-window considering the 14 days prior the exacerbations. Daily values of the CAT score and of the physical activity, heart rate, heart rate variability, temperature, respiration rate, cough frequency, and sleep pattern will be considered in the model.

The relation between the change of the patient self-assessed symptoms (CAT score) and the changes of the physical activity, heart rate, heart rate variability, temperature, respiration rate, cough frequency, and sleep pattern during the 3-month observation period will be further evaluated using linear spline regression to infer the location of the changepoints.

[figure not shown]
#### 3.4.5.5 Secondary Objective 5

To predict the CAT score and changes thereof by building a statistical model employing sensor-derived data and demographic and medical covariates

[figure not shown]
This analysis will be performed on the COPD participants set.

Similar to Primary Objective 2, different machine learning algorithms will be evaluated, and their performance will be assessed by estimating their accuracy, specificity, sensitivity, and area under ROC metrics. Other usual evaluation metrics such as precision, positive predictive value (PPV), negative predictive value (NPV), F1-score will be computed.

[figure not shown]
CCI

CCI

CCI

CCI

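### Objective 5 names no error measure in CAT points for the daily CAT total, and neither the cross-validation unit nor a reference predictor is stated

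*SAP*

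**What the plan says.** Protocol section 7 (Rationale and Background) sets two targets for the CAT. On the first it states that "the aim is to predict the total score (max = 40) from the sensor data". The second is a change of at least the MCID, which the same section puts at 2 points. It gives the purpose as well: "for the CAT/disease status prediction the aim is to reflect the daily status". Protocol 9.7.2.2 lists the targets as separate bullets, "patient self-assessed symptoms (CAT score measured on a daily basis" and "change of CAT score by 2 points or more (considered as MCID".

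SAP 3.4.5.5 covers the analysis of both targets by reference to the exacerbation model: "Similar to Primary Objective 2, different machine learning algorithms will be evaluated". On how these are to be scored, it says that "their performance will be assessed by estimating their accuracy, specificity, sensitivity, and area under ROC metrics". It adds: "Other usual evaluation metrics such as precision, positive predictive value (PPV), negative predictive value (NPV), F1-score will be computed". Protocol 9.7.2.2 gives the first four metrics only.

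In the visible text, neither document defines a cut-point or classes for the CAT total, or names a measure of error in CAT points or a reference predictor. Cross-validation appears only under Primary Objective 2 (SAP 3.4.5.2): "Internal cross-validation will be tested". The unit that is split is not stated.

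**The concern.** There are two separate gaps.

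**Metric.** Accuracy, sensitivity, specificity, AUC, precision, PPV, NPV and F1 all need a class label. For exacerbation yes/no, or for a 2-point change, that label exists. For a 0-40 score it does not, so the plan can be followed only by cutting the score at an unstated point. The result then says how often the model falls on the right side of that cut. It does not say how many points it is wrong, which is what a reader needs in order to set it against the 2-point MCID.

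**Reference and split.** The model is meant to follow the state of a participant from day to day. Each participant supplies about 90 daily scores, and the predictors include demographic and medical covariates that do not change over those days. If days of one participant fall in both training and test folds, a model can do well by learning that participant's usual level. Even with whole participants held out, covariates related to the usual level can produce a good overall score without any daily tracking. No stated comparison would separate these cases from real day-to-day prediction.

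At stake is how the Objective 5 result is read, and which model is taken into the later validation studies that the protocol foresees.

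**Working it through.** **The plan's own figures.** No target or threshold is stated for Objective 5. The only calculation (SAP 1.3.2, Protocol 9.5) is for exacerbation prediction, and it reproduces:
- With 18 events and a one-sided exact 95% lower limit of at least 0.50, 13 detections are needed. At true sensitivity 0.85 the probability of this is 0.958.
- P(X ≥ 18) for a Poisson mean of 30 is 0.993; 30/0.5 = 60; 60/0.9 = 66.7, so 67.

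Only the 60 participants are used below.

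**Check 1: what the named metrics miss.** Assumed: 5,400 scores (60 × 90), normal with mean 20 and SD 7, rounded and limited to 0-40, with the class being CAT above 20. Predictor p is the true score plus noise of SD 3. Predictor q = 20.5 + 0.1(p − 20.5). Predictor w = 20.5 + 2(p − 20.5). Both keep the ranking of p and its side of the 20.5 decision point, so accuracy and AUC cannot change.

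| Predictor | Accuracy | AUC | MAE | RMSE | R² |
|---|---|---|---|---|---|
| p | 0.877 | 0.953 | 2.41 | 3.04 | 0.81 |
| q | 0.877 | 0.953 | 5.06 | 6.31 | 0.18 |
| w | 0.877 | 0.953 | 7.34 | 9.23 | −0.75 |

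The largest MAE is 7.34/2.41 = 3.0 times the smallest, with the same result on both metrics.

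**Check 2: how far a participant's own earlier CAT goes without sensors.** The reference is the mean CAT of Days 8-14, the window that Protocol 9.3 uses for sensor baseline, predicting Days 15-91. Assumed, not in the documents: total SD 6, day-to-day autocorrelation 0.5 within participant, cut at the assumed mean of 18, and between-participant share s of the variance.

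- Variance of the 7-day mean, in units of the within-participant variance: [7 + 2 Σ(7 − k)0.5^k]/49, k = 1 to 6, = (7 + 10.03)/49 = 0.348.
- Mean covariance of that average with a later day: (1/7)(1.984)(1.000)/77 = 0.0037.
- Squared-error factor: 1 + 0.348 − 2(0.0037) = 1.340.
- R² = 1 − 1.340(1 − s). MAE = 0.798 × 6 × √[1.340(1 − s)].
- Accuracy = 0.5 + arcsin(r)/π, where r = [s + 0.0037(1 − s)]/√[s + 0.348(1 − s)].

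| s | r | Accuracy | R² | MAE |
|---|---|---|---|---|
| 0.2 | 0.294 | 0.59 | −0.07 | 5.0 |
| 0.4 | 0.516 | 0.67 | 0.20 | 4.3 |
| 0.6 | 0.700 | 0.75 | 0.46 | 3.5 |
| 0.8 | 0.859 | 0.83 | 0.73 | 2.5 |

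Simulated cohorts of 60 participants over 91 days give accuracy of about 0.59, 0.67, 0.75 and 0.83, and R² of about −0.09, 0.18, 0.45 and 0.72. This check shows persistence of the CAT. It does not show that sensors recognise participants.

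**Check 3: can uninformative sensors look good?** Assumed: 60 participants, 90 days, 17 sensor variables (the number in SAP 3.4.5.3) unrelated to CAT, 70% of sensor variance between participants, CAT mean 20 and SD 7, a 10-nearest-neighbour model, and a cut at CAT above 20. Values are for s = 0.5 / 0.7 / 0.9.

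| | AUC | R² | Within-participant correlation |
|---|---|---|---|
| Sensor model, folds by day | 0.80 / 0.88 / 0.95 | 0.42 / 0.65 / 0.86 | −0.03 / −0.03 / −0.02 |
| Own training mean | 0.82 / 0.90 / 0.96 | 0.48 / 0.70 / 0.90 | not applicable |
| Sensor model, folds by participant | 0.49 / 0.51 / 0.51 | −0.25 / −0.29 / −0.36 | 0.00 / 0.00 / 0.01 |

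R² is inflated under day-level folds too. The artefact therefore comes from the split and the missing reference, not from the type of metric.

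**The case against.** The other side has several good arguments.

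- **The change target.** A change score removes the participant's stable level, so performance on it is not explained by knowing who the participant is. The named metrics suit this target. This stands, and the point is confined to the total.
- **The list is open.** The wording of the second metric list allows additions. This stands in part: nothing is excluded, but every named item is a classification metric.
- **Objective 4.** SAP 3.4.5.4 plans a mixed model of CAT on sensor values and of change on change, a daily analysis in the 14 days before exacerbations, and splines. This is relevant evidence on association within participants. Its random effects are only possible inclusions, though, and it does not score the Objective 5 predictions.
- **Hidden material.** Figures and redacted text lie next to SAP 3.4.5.5, and the TLF plan content is not visible. A benchmark could be there. The metric paragraph itself is intact and agrees with Protocol 9.7.2.2.
- **Variance shares.** No passage says that daily CAT varies mainly between participants. At a share of 0.2 the own-mean reference is weak (R² below zero). This stands, which is why the range is shown.
- **A stricter question.** The documents ask for an objective reflection of disease status. They do not ask the model to beat the participant's own questionnaire. This stands, so the references belong in the report as context.
- **Exploratory status.** Protocol section 7 requires later validation of any model, and Objective 5 is secondary with no success threshold. This limits the consequence without removing it.

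**Conclusion.** The point holds for the CAT total, on the visible text. No named metric measures error in CAT points; Check 1 shows a threefold range of MAE (2.4 to 7.3 points) at identical accuracy and AUC, against a 2-point MCID. Separately, neither the fold unit nor a reference predictor is stated, so good performance on the total could reflect stable differences between participants. How much this matters depends on the between-participant share, which the documents do not give: from 0.2 to 0.8, the own Day 8-14 mean gives accuracy of about 0.59 to 0.83. All the simulated values show the mechanism and are not forecasts for this study.

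A reader might infer that Objective 5 as a whole cannot tell daily prediction from identification of the participant, or that the choice of metrics causes this. The documents do not support that: the change target is served by its metrics, the metric list is open, Objective 4 adds evidence on association, and the recognition artefact depends on the split and the reference. The consequence is limited to how the model is interpreted and carried forward. The change is worth making before the analysis.

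**What to change.** In SAP 3.4.5.5, separate the two targets.

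- **CAT total:** report out-of-fold MAE and RMSE in CAT points, with all days of a participant in one fold, and the within-participant correlation of predicted and observed CAT. Score observed CAT days only, because SAP 3.4.4 allows CAT to be imputed for machine learning, by LOCF among other methods.
- **References:** report the same error measures, on the same days, for the participant's own Day 8-14 CAT mean, the last observed CAT and a covariates-only model. State that these give context and are not a success threshold.
- **Change of 2 points or more:** keep the classification metrics, with the same grouped folds.

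The cost is SAP wording and a few extra statistics from data already collected; no visits or participants are added. Reported performance may look less favourable than under day-level folds without references.

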#### *3.4.5.10 Analysis of safety outcomes*

##### Adverse device effects

There is a very low likelihood for ADEs to occur in this study. Any such events will be reported in a listing, containing Subject ID, Site ID, Sex, Age, COPD Severity, Reported Term, Preferred Term, System Organ Class, Serious Flag, Severity, Outcome. ADEs are collected in both cohorts.

#### Adverse events

Adverse events are continuously collected throughout the observation period in both cohorts. A frequency table will describe AE occurrence by severity.

Proportions of AE will be reported by preferred term and system organ class according to WHO MedDRA dictionary (latest version).

#### *3.4.5.11 Other outcome analyses*

##### COPD exacerbations

For COPD exacerbations, a histogram will be provided showing color-coded occurrence counts of mild, moderate and severe exacerbations by day during the 3-month observation period. In addition, descriptive statistics for exacerbation occurrence and duration will be provided, stratified by severity.

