9.1.2.1 Primary Outcomes

The primary objective is to 1) describe the distribution of sensor collected data with COPD exacerbations, as well as 2) to predict COPD exacerbations by building a statistical model.

Severity of acute exacerbations of COPD (AECOPD) are defined using the GOLD definitions based on treatment consequences (event-based) ([Vogelmeier 2017](#)): AECOPDs are defined as “an acute worsening of respiratory symptoms that results in additional therapy”. Exacerbations are classified as 1) **mild** if they are treated with short-acting bronchodilators only; 2) **moderate** if they are treated with short-acting bronchodilators plus antibiotics and/or oral corticosteroids; or 3) **severe** if the patient visits the emergency room or requires hospitalization because of an exacerbation.

The occurrence of exacerbations during the observation period will be defined as follows:

- For moderate/severe exacerbation requiring a physician’s intervention, emergency room visit or hospitalization, the severity, date of the exacerbation, and the duration of the exacerbation will be recorded via an eCRF.
- For mild exacerbations: self-reported; treated by the participant without intervention by a physician will be documented in the patient application labeling section (days with added treatment).

The duration of exacerbations during the observation period will be defined as follows:

The duration of a severe/ moderate exacerbation will be derived from the duration of added medication from the group of systemic corticosteroids and/or antibiotics which define moderate exacerbations by GOLD. Days in-hospital for severe exacerbations will also be captured.

The duration of mild exacerbations will be derived from the event “additional relieve medication taken” noted in the labelling section of the patient facing applicaton (which defines mild exacerbations). Duration and start / stop will be derived from these patient entries.

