9.2.3 Observation Period

Participants will be followed-up for 3 months (until End of Study visit) or until premature discontinuation from study, whichever occurs first.

Participants in the calibration cohort will be followed-up for 2 weeks.

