9.2.4 Frequency of Assessments

An overview of the planned assessments is provided in [Table 4](#) and [Table 5](#).

Company substance code INN
MS202559_0001

COPD cohort

The participants will visit the sites as per routine practice and the timing of the visits and assessments performed will be as per the treating physician judgment. Results of the assessments will be collected upon availability.

Table 4 Planned Assessments: COPD Cohort

Assessments	Baseline Visit Day 0	Exacerbation Visits (moderate and severe)	End of Study 3 Months ± 14 days	Comments
Participant Informed consent	X			
Inclusion/Exclusion criteria	X			
Demographics	X			
Medical history	X			
Physical examination	X	X	X	
COPD history	X			
Baseline Medication	X			
Record changes in medication (COPD and other)		X	X	Changes in medication means changes of medication at the time of the current visit (including newly prescribed medication) as compared to the baseline visit (Day 0)
Comorbidities	X			
Smoking status	X			
Exacerbation history	X			
Moderate and severe exacerbations during observation period		X	X	Moderate and severe exacerbations should be recorded that occurred between Day 0 and the current visit (including exacerbations at the time of the visit)
Lung function (Plethysmography)	X	X	X	For the Baseline visit (Day 0), data from the past 2 weeks are acceptable.
End of study satisfaction questionnaire			X	
(S)AE recording	→			Continuous recording
Serious Adverse Device Effects (SADE) and Device Deficiency (DD) reporting	→			Continuous reporting
CAT collection via App	Daily at home			
Data collection via App (labeling events and activities)	Daily at home			Includes medication data used to identify mild exacerbations

Laboratory values (if available from clinical practice)				For the Baseline visit (Day 0), data from the past 2 weeks are acceptable.
C-reactive protein (CRP)	X	X	X	
Procalcitonin	X	X	X	
Blood count (including eosinophiles, neutrophiles, Hb)	X	X	X	
Capillary blood gas analysis: pO ₂ and pCO ₂ ; SpO ₂	X	X	X	

Table 5 Planned Assessments Calibration Cohort

Assessments	Day 0	End of Study 2 Weeks	Comments
Participant informed consent	X		
Inclusion/Exclusion criteria	X		Assessed by Investigator by review of medical history and/or participant reported medical history
Demographics	X		
Medical history	X		
Comorbidities	X		
Medication	X	X	
End of Study satisfaction questionnaire		X	
(S)AE recording	→		Continuous recording
SADE and DD reporting	→		Continuous reporting

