The Investigator must promptly respond to any request by the CRO for follow-up information or questions from the Sponsor or delegate. Such requests will be sent to the Investigator via the CRO. AEs and SAEs occurring during the study must be monitored and followed up by the Investigator until stabilization or until the outcome is known unless the participant has a fatal outcome or is lost to follow-up. All events that are still ongoing at the end of the observation period will continue to be documented as such.

The Investigator will ensure any necessary additional therapeutic measures and follow-up procedures are recorded and reported via a follow-up SADE/DD Report Form. Reasonable attempts to obtain follow-up information must be made and documented.

Company substance code **INN**
MS202559_0001

Reporting of any new information on a previously reported event (follow-up) will follow the procedures and timelines of the original report.

The CRO must forward the follow-up information within 72 hours to Global Patient Safety and to the manufacturer of the medical device, as noted above for initial reports.

11.6 Safety Reporting to the Competent Authorities and IEC/IRBs.

The Sponsor or authorized designee reports to the Competent Authorities (CA) any reportable event defined in Section [11.5](#).

The period for reporting must take account of the severity of the event:

- For all reportable events which indicate an imminent risk of death, serious injury, or serious illness and that requires prompt remedial action for other patients, users or other persons or a new finding to it: Immediately, but not later than 2 calendar days after awareness by the Sponsor or authorized designee of a new reportable event or of new information in relation with an already reported event.
- This includes events that are of significant and unexpected nature such that they become alarming as a potential public health hazard. It also includes the possibility of multiple deaths occurring at short intervals.
- Any other reportable events or a new finding/update to it: Immediately, but not later than 7 calendar days following the date of awareness by the Sponsor or authorized designee of the new reportable event or of new information in relation with an already reported event.

Where necessary to ensure timely reporting, the sponsor or authorized designee may submit an initial report that is incomplete followed up by a complete report.

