## 2.3 OUTCOME DEFINITIONS

### 2.3.1 Outcomes for primary objectives

The primary outcomes are based on COPD exacerbations. Exacerbations are classified as

- 1) mild if they are treated with short-acting bronchodilators only,
- 2) moderate if they are treated additionally with antibiotics or oral corticosteroids, or
- 3) severe if the patient visits the emergency room or requires hospitalization because of an exacerbation.

The occurrence of exacerbations during the observation period is measured as follows.:

- For moderate/severe exacerbation requiring a physician's intervention, exacerbation details will be recorded via eCRF by the clinical site. Severity, onset and duration will be derived according to the definition above from the documented COPD medication associated with the patients' exacerbation visit. The definition details for COPD medication and ATC codes will be finalized during the planned Data review meeting prior to the final analysis.
- For mild exacerbations: self-reported; treated by the participant without intervention by a physician will be documented in the patient application labeling section (days with added treatment: short-acting bronchodilators only). The start date and end date of addition of short-acting bronchodilators can thus be retrieved from the patient application. The documented use of additional medication (Bedarfsmedikament) will be considered as a mild exacerbation with the following rules for start and end days:
  - A mild exacerbation must start with at least 2 consecutive days of additional medication reported, the first day of consecutive medication will determine the start of the exacerbation.
  - If there are gaps in the additional medication reporting, a maximum of 2 days is allowed to be considered only one exacerbation. A minimum of 70% of the days must have additional medication reported. The end date of the exacerbation is the last day where both these rules are fulfilled.
- Any exacerbations that happen within 5 days will be considered as overlapping, as well as exacerbations that have an intersection in their start and end dates. Overlapping exacerbations will be considered as only one and classified as the graver one. (4)
  - If all overlapping exacerbations have the same type, the start date is the start date of the first exacerbation, and the end date of the last one.

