#### 3.4.1 General specifications

Descriptive statistics will be provided for study variables and measurement time points as specified in the following sections. Unless indicated otherwise, descriptive statistics will include the number of observations and missing values, means, standard deviations, medians, interquartile range, Q1, Q3, minimum, and maximum. Results for continuous variables (e.g., age at diagnosis) and correlation coefficients will be reported with at least 3 figures as rounded numbers with 2 decimal values. Descriptive statistics for categorical variables will report n (%), missing and with number (n) equal to the total number of patients at each category level (without missing) during the assessment period and will be reported with 3 figures as percent with 1 decimal value.

Medical history, adverse events and prior/concomitant medication will be summarized using coded preferred terms by proportion of patients with at least one occurrence relative to the number of patients in the cohort.

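### Exacerbation duration has no rule for episodes still open when observation stops; mild episodes are then cut short and look complete

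*SAP*

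**What the plan says.** SAP 3.4.5.11, under COPD exacerbations, plans that "descriptive statistics for exacerbation occurrence and duration will be provided, stratified by severity". SAP 3.4.1 defines what that means: "descriptive statistics will include the number of observations and missing values, means, standard deviations, medians, interquartile range, Q1, Q3, minimum, and maximum". No method for censored durations and no count of open episodes is planned.

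Observation has a fixed end. Protocol 9.2.3: "Participants will be followed-up for 3 months (until End of Study visit) or until premature discontinuation from study, whichever occurs first". Protocol 9.1.1 adds that death also ends the study and that the devices, including the phone with the app, go back at End of Study.

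The source of the duration depends on severity:

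- **Mild.** Protocol 9.1.2.1 relies on the app alone: "Duration and start / stop will be derived from these patient entries". Under SAP 2.3.1 an episode starts with two consecutive days of additional medication, tolerates gaps of at most 2 days, and needs medication on at least 70% of its days. It ends on the final day on which the gap and 70% conditions both hold.
- **Moderate and severe.** Protocol 9.1.2.1: "The duration of a severe/ moderate exacerbation will be derived from the duration of added medication from the group of systemic corticosteroids and/or antibiotics". SAP 2.3.1: "Severity, onset and duration will be derived according to the definition above from the documented COPD medication associated with the patients' exacerbation visit".

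Open episodes are foreseen. In Protocol Table 4 (9.2.4), the row for moderate and severe exacerbations covers the End of Study visit and applies to past events, "including exacerbations at the time of the visit". For adverse events, Protocol 11.5 says: "All events that are still ongoing at the end of the observation period will continue to be documented as such".

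**The concern.** A duration can be summarised with an ordinary mean and quartiles only if its end was seen. SAP 2.3.1 has detailed start, gap and overlap rules but is silent on an episode that is running when data stop.

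The problem is clearest for mild episodes. Their end-date rule always returns a date, so an episode in progress at device return gets an end at or near the last app day. It enters the table as a completed, shorter episode, and the missing-value count in SAP 3.4.1 does not reveal it.

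For a moderate or severe episode without a documented stop date, the SAP does not say whether the duration is cut at the last contact or left missing.

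What is at stake is the accuracy of one descriptive result. Duration by severity is part of secondary outcome 3c.

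**Working it through.** **Plan's own figures.** The documents give no exacerbation duration and no expected share of open episodes, so there is no figure of that kind to reproduce. The one relevant count is the 30 expected moderate or severe events (SAP 1.3.2): 60 participants × 0.5 events = 30. This reproduces, as does the enrolment target: 60 / 0.9 = 66.7, rounded up to 67. No expected number of mild episodes is given.

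**Assumptions.** Follow-up is T = 91 days (3 months) and onset is uniform over follow-up. The true mean duration m is 5 to 14 days, with 21 as an extreme. The shape runs from fixed length (no spread) through gamma with shape 2 to exponential.

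**Formulas.** For durations short relative to T:

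- share open ≈ m / T
- mean if cut at study end, fixed length: m − m²/(2T)
- mean if cut at study end, exponential: about m − m²/T

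Worked case, m = 7: share open 7/91 = 7.7%. Fixed length: 7 − 49/182 = 6.73, which is 3.9% short. Exponential: 7 − 49/91 = 6.46, about 7.7% short.

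A simulation of 2,000,000 episodes per setting agrees with the formulas:

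| Assumed mean (days) | Share open | Per 30 events | Mean if cut (fixed to exponential) | Mean if open episodes dropped (fixed / gamma / exponential) |
|---|---|---|---|---|
| 5 | 5.5% | 1.6 | −2.7% to −5.5% | 0% / −2.9% / −5.8% |
| 7 | 7.7% | 2.3 | −3.9% to −7.8% | 0% / −4.1% / −8.5% |
| 10 | 11% | 3.3 | −5.5% to −11.0% | 0% / −6.2% / −12.3% |
| 14 | 15.4% | 4.6 | −7.7% to −15.4% | 0% / −9.2% / −18.0% |
| 21 | 23% | 6.9 | −11.5% to −22.7% | 0% / −14.8% / −27.7% |

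The column for cut episodes is the one that applies to mild episodes, because their rule always supplies an end date. The dropped column can apply only to moderate and severe episodes with no stop date. If the actual stop date is obtained after study end, the bias is 0%.

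**Sensitivity.** With m = 14 and exponential durations, the understatement when cut is 18.2% at 77 days of follow-up and 13.4% at 105 days, the limits of the ±14-day visit window. Adding 10% withdrawal at uniform times changes little: for gamma durations with m = 7, 8.1% are open and the cut mean is 6.1% short, against 7.7% and 5.7% without withdrawal.

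**Differences between severity classes.** Take true means of 7 and 14 days, a true gap of 7.0.

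- Both classes cut, exponential: (14 − 196/91) − (7 − 49/91) = 11.85 − 6.46 = 5.4 days.
- Both cut, fixed length: (14 − 196/182) − (7 − 49/182) = 12.92 − 6.73 = 6.2 days.
- Only the 7-day class cut (as if it were mild), the other fully observed, exponential: 14 − 6.46 = 7.5 days.

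The gap can shrink or widen, depending on which classes lose their end dates.

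**The case against.** The best defence concerns moderate and severe episodes. Their duration comes from documented medication, and medication changes are recorded at the End of Study visit. Protocol 11.4 asks for onset and resolution dates of adverse events, and Protocol 11.5 requires follow-up until stabilisation or a known outcome. An end date can therefore become known after observation closes. This stands as a limit on the point. It does not close the gap, because no text links adverse-event follow-up to exacerbation duration, and the same section has open events recorded as ongoing. It does not help mild episodes, which have no source after the phone is returned.

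A reader might infer that all durations are biased short, most of all in the longest-lasting severity class, so that the reported difference between classes shrinks. The documents do not support this. They give no duration for any class and so no ranking. Dropping open episodes of fixed length causes no bias. If only mild episodes are cut and they are the shorter ones, the difference widens. No comparison of duration between classes is planned in any case.

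It is also fair that little depends on this table. The protocol calls the study exploratory. The objective 3 analysis in SAP 3.4.5.3 correlates exacerbation counts, not durations. The primary prediction model uses onset, and the sample size uses event counts. SAP 2.3.1 defers medication definitions to the data review meeting, where some of this might be settled, but it does not mention open episodes.

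**Conclusion.** The point holds as a minor defect. The SAP treats duration as always complete and has no rule for episodes open at End of Study, withdrawal or death. For mild episodes the plan as written understates duration without any visible sign. For moderate and severe episodes a bias arises only where no stop date is obtained, and its size then depends on whether the episode is cut or dropped.

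Under assumed means of 5 to 14 days and uniform onset over 91 days, about 5% to 15% of episodes would be open. The mean would be understated by about 3% to 15% if they are cut at study end. These figures rest wholly on the assumed durations. No direction can be claimed for differences between severity classes, and the primary results are unaffected.

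**What to change.** In SAP 2.3.1, define and flag episodes without an observed end:

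- **Mild:** the last medication day falls within the 2-day gap allowance of the participant's last app day, so the episode cannot be confirmed as over.
- **Moderate or severe:** no treatment stop date is documented.

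In SAP 3.4.5.11, report the number of flagged episodes by severity. Give the Kaplan-Meier median and quartiles of duration with flagged episodes right-censored at the last observed day. List episodes that end in death separately.

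The cost is a few sentences in the SAP and a standard procedure in R or SAS, with no new data. The downside is slightly more analysis work and imprecise estimates in classes with few events. There, the count of open episodes may be the more useful figure.
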